9.2 Subject Accountability

The number and percent of subjects who are enrolled (including the dates for the first subject enrolled and last subject completed study), receive investigational product, complete investigational product, discontinue from investigational product (including reasons for discontinuing), complete study, discontinue the study (including reasons for discontinuing) will be summarized by cohort.

9.3 Important Protocol Deviations

Important Protocol Deviations (IPDs) categories are defined by the study team before the first subject's initial visit and updated during the IPD reviews throughout the study prior to database lock. These definitions of IPD categories, subcategory codes, and descriptions will be used during the course of the study. Eligibility deviations are defined in the protocol. **IPDs and eligibility deviation will be summarized.**

9.4 Demographic and Baseline Characteristics

The following descriptive summaries of the demographic and baseline characteristics will be produced: Demographic (ie, age, age groups [**18 < 65, 65 to < 75, 75 to < 85, >= 85 years**], sex, race, and ethnicity) and baseline characteristics (**height, weight, disease type/sub-type, prior lines of therapy, and Eastern Cooperative Oncology Group [ECOG] Performance Status**) will be summarized using descriptive statistics. If multiple races have been reported for a subject, the subject will be categorized as multiple.

9.5 Efficacy Analyses

Table 2. Efficacy Endpoints

Endpoint	Statistical Analysis Methods
Overall response rate	The proportion of subjects with response to treatment with corresponding 2-sided exact 95% CI will be calculated using the Clopper-Pearson method (Clopper and Pearson, 1934) for the Full Analysis Set. Refer Appendix B for code fragment.
DOR, PFS, and OS	Kaplan-Meier estimates and Kaplan-Meier curve will be provided for the Full Analysis Set.
TTR	Descriptive statistics will be provided for subjects with response.
MRD[-] status at CR (Parts 3B and 3C only)	Proportion of MRD[-] at CR will be provided for subjects with CR.

For time to event endpoints (including DOR, TTR, OS, and PFS), summary table or figure may not be generated if the number of events is less than 10. The individual subject-level data will be provided.

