## **10.6.3 Secondary Endpoints**

### **10.6.3.1 Efficacy Endpoint Analyses**

The analyses on PFS and OS will be done only using data from dose expansion subjects; other efficacy endpoints will be analyzed using data from both dose escalation and dose expansion.

The number and percentage of subjects by overall response and overall response category will be calculated and tabulated. Using the Kaplan Meier estimate, the PFS at 6 and 12 months and the OS at 6 and 12 months with corresponding 90% CI will be tabulated. Listings will be produced for all subjects indicating the OS, PFS, time to

Approved

response and duration of response. Kaplan Meier curve will be presented for OS, PFS, time to response and duration of response with estimates for rates and 80% CI at selected weeks.

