
 Estimate the maximum tolerated or recommended combination dose (MTCD) and/or recommended phase 2 combination doses (RP2CD) of AMG 397 	
Secondary	
Part 1 QD2 Monotherapy (MM, NHL, AML) – CLOSED TO ENROLLMENT	

 Evaluate the preliminary efficacy of AMG 397 monotherapy 	
 Overall response rate (ORR) using response criteria per the following: 
 International Myeloma Working Group – Uniform Response Criteria (IMWG-URC) for MM subjects Lugano Classification for NHL subjects Revised International Working Group (IWG) for AML subjects Revised IWG for MDS subjects progression-free survival (PFS) overall survival (OS) time to response duration of response (DOR)

 Evaluate the pharmacokinetics (PK) of AMG 397 	
 AMG 397 PK parameters including, but not limited to, maximum observed concentration (C_{max}), time of maximum observed concentration (T_{max}), area under the concentration time curve (AUC), clearance (CL) and half-life ($t_{1/2}$)

Part 2A QW Monotherapy (MDS, AML), Part 2B QW Monotherapy (AML), and Part 2C QW Monotherapy (MM)
	

 Evaluate the preliminary efficacy of AMG 397 monotherapy (For Part 2B: Japan subjects only) 	
 ORR using response criteria per the following: 
 Revised IWG for AML subjects Revised IWG for MDS subjects IMWG-URC for MM subjects PFS OS time to response DOR

 Evaluate the PK of AMG 397 	
 AMG 397 PK parameters including, but not limited to, C_{max}, T_{max}, AUC, CL, and $t_{1/2}$

Part 3 QW Combination Therapy (MDS, AML, MM)
	

 Evaluate the preliminary efficacy of AMG 397 combination therapy 	
 OR based on investigator assessment per: 
 Revised IWG for MDS subjects 2017 European LeukemiaNet (ELN) criteria in AML subjects IMWG-URC for MM subjects PFS OS time to response DOR

 Evaluate the PK of AMG 397 and azacitidine (Parts 3A and 3B) or dexamethasone (Part 3C) when administered in combination 	
 PK parameters for the combination including, but not limited to C_{max}, AUC, CL, and $t_{1/2}$

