3.2 Sample Size

Up to 240 subjects will be enrolled in the study. A total of 24 subjects were enrolled during Part 1 dose escalation (12 in both Part 1A and Part 1B). Up to 26 evaluable subjects will be enrolled into Parts 2A and 2C monotherapy dose escalation part and up to 20 evaluable subjects into Part 2A (MDS only) dose expansion. Up to 6 subjects will be enrolled into Part 2B. Up to 78 evaluable subjects will be enrolled into each of the combination therapy dose escalation parts (up to 26 each for Parts 3A, 3B, and 3C) and up to 60 evaluable subjects (up to 20 subjects each for 3A, 3B, and 3C) in dose expansion.

The sample sizes are based on practical considerations and it is consistent with conventional oncology studies with the objective to identify the MTC. With 10 subjects, there is a 40% to 65% probability of observing at least 1 adverse event if the true event rate is 5% to 10%. Exact 95% binomial CI will be provided for ORR. With the 20 subjects in each dose expansion group and a 20% ORR, the 2-sided 95% exact CI would be 6% to 44%.

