- **IMWG-URC for MM**
- **2017 ELN criteria for AML**
- **Revised IWG for MDS**
- **Lugano Classification for NHL**

Dose Limiting Toxicity (DLT)

Unless otherwise specified, investigators determine whether an adverse event qualifies as a DLT per the definition described in the protocol.

DLT Observation Period

The DLT observation period is defined as, at minimum, 28 days after the initial dose of AMG 397. If lead-in dosing period is initiated, the DLT-observation period is defined as the amount of time for subject(s) for each dose cohort to receive at least 1 week of lead-in dose and 3 weeks of target dose.

Duration of Response (DOR)

Duration of response is calculated for subjects who have achieved response (PR or better). It is defined as time from the first observation indicating a response to the subsequent date of disease progression or death, whichever is earlier.

DOR time in months: (date of disease progression or death - date of the first observation of response +1)/30.4

Subjects without disease progression or death until the analysis data cut-off date will be censored at the last adequate disease assessment date.

Fridericia-corrected QT Interval (QTcF)

The Fridericia correction will be calculated from the investigator reported QT (msec) and RR interval (msec): $QTcF = QT / (RR/1000)^{1/3}$

Investigational Product (IP)

IP is used in reference to AMG 397.

Overall Response Rate (ORR)

ORR is the incidence of either PR or better based on investigator assessment. All subjects that do not meet the criteria for response (PR or better) by the analysis cutoff date will be considered as non-responders.

Progression-free survival (PFS)

PFS time is calculated as time from first dose of IP date to disease progression date or death due to any cause, whichever is earlier.

PFS time in months: (date of disease progression or death - first dose of IP date +1)/30.4

Subjects without disease progression or death until the analysis data cut-off date will be censored at the last adequate disease assessment date. If no post-baseline disease assessment, censoring is at the first dose of IP date.

Overall survival (OS)

OS is defined as the time from first dose of IP date until death due to any cause.

OS time in months: (date of death - first dose of IP date +1)/30.4

Patients without event will be censored at their last date known to be alive.

Study Day

Post study day 1: study day = (date –Study Day 1) + 1

Pre study day 1: study day = (date –Study Day 1)

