9.1 General Considerations

Descriptive statistics on continuous data will include means, medians, standard deviations and ranges, while categorical data will be summarized using frequency counts and percentages. Graphical summaries of the data may also be presented. When data are summarized by time, the values recorded against the scheduled time points listed in the protocol will be used. When assessing minimum/maximum increases or decreases over the study, all assessments, including unscheduled assessments will be used.

For each indication, efficacy and safety data will be summarized by dose level.

For the subjects who complete the DLT period and proceed to a higher dose level or crossover to a combinational therapy cohort for the following treatment cycle,

efficacy and safety data will be summarized per their initial assigned dose level.

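### Kaplan-Meier OS is planned on a set that includes up to 24 Part 1 escalation subjects, for whom the supplied protocol schedules no survival follow-up; confirm the follow-up and, if there was none, restrict OS by study phase

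*SAP*

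**What the plan says.** **SAP.** Table 2 in Section 9.5 says of DOR, PFS and OS that "Kaplan-Meier estimates and Kaplan-Meier curve will be provided for the Full Analysis Set". Section 6.1 defines that set as every enrolled subject given at least one dose, with no limit by part or phase. Section 2.1 lists OS among the Part 1 secondary endpoints, so Part 1 is meant to be included. Section 3.2 gives the numbers: "A total of 24 subjects were enrolled during Part 1 dose escalation (12 in both Part 1A and Part 1B". Under the OS definition in Section 5, "Patients without event will be censored at their last date known to be alive".

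Three SAP provisions limit what will be shown. Section 9.1: "For each indication, efficacy and safety data will be summarized by dose level". Section 9.5, on time-to-event endpoints: "summary table or figure may not be generated if the number of events is less than 10". The same paragraph then adds: "The individual subject-level data will be provided".

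**Supplied protocol.** Section 10.6.3.1 restricts the population: "The analyses on PFS and OS will be done only using data from dose expansion subjects". The Synopsis (Procedures), Section 3.5.1, Section 7.4.5 and footnotes 6 and 26 to the schedule of assessments all confine long-term survival follow-up to dose expansion. It runs every 3 months, up to 1 year from first dose. For an escalation subject, the last scheduled visit is the safety follow-up in Section 7.4.4, 28 (+7) days after the last dose.

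**Versions.** SAP Section 1 names protocol Amendment 4, dated 09 December 2020. The last change log in the supplied protocol is Amendment 1. SAP Section 10 declares no changes from the protocol.

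**The concern.** Kaplan-Meier assumes that subjects censored at a given time have the same prognosis as those still followed. Protocol 6.2.1.3 has subjects stop AMG 397 for reasons that include progression, dose-limiting toxicity and clinical deterioration. If contact ends about a month later, a subject still alive is censored shortly after an event that may carry a worse prognosis. Later deaths are not seen, and the curve is carried by subjects who are still on treatment. If the death hazard rises after stopping, a Part 1 OS estimate is too high.

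What is at stake is the reading of a descriptive secondary endpoint. No hypothesis is tested (SAP 2.2), and dose decisions do not use OS.

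**Working it through.** **1. Numbers in the plan.** Part 1: 12 + 12 = 24. This is a maximum for the Full Analysis Set, which also requires a dose. The planned total is reproduced as 24 + 2×26 + 20 + 6 + 78 + 60 = 240, if the figure of 26 applies to Parts 2A and 2C separately. Part 1 is then 24/240 = 10% at full accrual.

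**2. Censoring time under the supplied protocol.** Doses fall on two consecutive days each week, so the last dose of cycle 1 is on day 23 and of cycle 6 on day 28×5 + 23 = 163. For a subject alive at safety follow-up, using the SAP's 30.4-day month:

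- after 1 cycle: (23 + 28)/30.4 = 1.7 to (23 + 35)/30.4 = 1.9 months
- after 6 cycles: (163 + 28)/30.4 = 6.3 to (163 + 35)/30.4 = 6.5 months
- dose expansion, for comparison: 365/30.4 = 12.0 months

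Deaths up to safety follow-up are observed and count as events.

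**3. Size of the bias.** The documents give no on-treatment survival or treatment-duration figures for this drug, so the inputs are assumptions:

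- time to stopping treatment: exponential, median 2 or 4 months (rate g)
- on-treatment death hazard h: median survival 8, 12 or 18 months
- hazard after stopping: r×h, with r = 1, 2 or 4
- censoring: d = 28 or 35 days after stopping

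With k = g + h − rh:

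- True survival: S(t) = exp(−(g+h)t) + (g/k)·exp(−rht)·(1 − exp(−kt)).
- Kaplan-Meier: no one is censored before d. After d, the ratio of recently stopped to on-treatment subjects at risk is q = (g/k)(exp(kd) − 1). The hazard that Kaplan-Meier sees is h(1 + rq)/(1 + q), so its limit is S(d)·exp(−h(1 + rq)(t − d)/(1 + q)).

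Example: median treatment 2 months (g = 0.3466), median survival 12 months (h = 0.0578), d = 28/30.4 = 0.921 months, t = 6.

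- r = 2: k = 0.2888, g/k = 1.2. True S(6) = 0.0884 + 1.2×0.5×0.8232 = 0.582. q = 0.366, hazard seen = 0.0732, S(d) = 0.941. Kaplan-Meier = 0.941×exp(−0.0732×5.079) = 0.649. Bias +6.6 points.
- r = 4: k = 0.1733, g/k = 2. True S(6) = 0.0884 + 2×0.25×0.6464 = 0.412. q = 0.346, hazard seen = 0.1023, S(d) = 0.928. Kaplan-Meier = 0.928×exp(−0.1023×5.079) = 0.552. Bias +14.0 points.

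Over all combinations (simulation, 400,000 subjects per cell, within about 0.1 point of the formulas):

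| Hazard ratio r | Pooled Part 1 only | All parts, 10% unfollowed |
|---|---|---|
| 1 | about 0 | about 0 |
| 2 | +3.5 to +7.7 points | +0.2 to +0.4 |
| 4 | +8.4 to +14.0 points | +0.5 to +0.7 |

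**4. Would a Part 1 curve reach 10 events?** An indication-by-dose cell with fewer than 10 subjects cannot. For the 12 AML subjects (Part 1B, all doses together), with p the chance that a death is observed, P(at least 10 of 12) = 66p¹⁰(1−p)² + 12p¹¹(1−p) + p¹².

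- Medians of 8 to 18 months: p is 0.13 to 0.53, so the chance is 0 to 3%.
- Protocol 2.1.3 cites a median OS of 3.8 months in AML refractory to one high-dose cytarabine course. It is not an on-treatment median, but it is a reasonable low anchor. Used as one, with the longest follow-up combination (median treatment 4 months, 35 days), p = 0.60, 0.67 and 0.78 at r = 1, 2 and 4. The chance is then about 8%, 19% and 48%.

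The 10-event threshold therefore cannot be relied on to suppress a pooled AML curve.

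**The case against.** The strongest objection is that the governing protocol is missing. The SAP differs from the supplied protocol in ways that can only come from later amendments: 240 subjects against 90, 95% against 80% intervals for ORR, and mTPI for Parts 2 and 3. The expansion-only restriction on OS may have gone as well, and SAP Section 10 suggests that Amendment 4 agrees with the SAP. This stands. A reader might infer that the SAP contradicts its own protocol, or that Section 10 is wrong; the documents do not show either. They show that Part 1 closed to enrolment and the trial was put on hold in July 2019, before the December 2020 amendment. That makes missing Part 1 survival follow-up plausible, not proven.

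Second, little may reach a reported estimate. Summaries are by indication and dose level, output may be omitted below 10 events, and subject-level data are promised in any case. This stands as a limit on impact. The omission rule is discretionary, however, and it looks at the event count rather than at follow-up.

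Third, survival data may exist anyway. Protocol 8.1 presses for subjects who stop treatment to stay on study, and 12.4 allows a search of public records. Neither schedules survival contact, and the 12.4 search concerns subjects who withdraw before finishing their required visits.

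Fourth, some Part 1 subjects may have stopped because of the hold rather than because of prognosis. That would reduce any bias.

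**Conclusion.** The point holds conditionally and is minor. On the supplied documents, SAP Table 2 puts OS on a population that includes up to 24 subjects with no scheduled survival follow-up. If no later amendment added it, Part 1 subjects alive at safety follow-up may be censored there, often after stopping for progression, toxicity or deterioration.

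Bias requires a second condition, a higher death hazard after stopping. The figures of +3.5 to +7.7 points (ratio 2) and +8.4 to +14.0 points (ratio 4) rest on the assumed medians of 8 to 18 months. They describe a pooled Part 1-only 6-month estimate that no passage specifically plans. An all-parts estimate would move by less than 1 point.

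Two stronger readings are not supported. One is that every Part 1 subject is lost soon after treatment: deaths up to safety follow-up are events, and only survivors at last contact are affected. The other is that OS in Parts 2 and 3 shares the problem: follow-up for those parts is set in an amendment that was not supplied, and nothing is concluded about them.

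**What to change.** 1. Confirm whether Part 1 subjects had scheduled survival follow-up under the protocol versions in force for Part 1. If they did, cite the provision in the SAP and the point is closed.
2. If they did not, restrict Kaplan-Meier OS in SAP Table 2 to subjects who had scheduled survival follow-up. Define them by study phase (escalation or expansion), not by part: the supplied follow-up rule works by phase, and Parts 2A and 3A to 3C each contain both.
3. Report Part 1 OS through the subject-level data already planned in SAP 9.5.
4. Declare in SAP Section 10 any difference in OS population from the protocol in force.

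The cost is SAP wording only. The downside is that there would be no OS curve for Part 1.

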9.6 Safety Analyses

9.6.1 Adverse Events

The Medical Dictionary for Regulatory Activities (MedDRA) version **23.1** or later will be used to code all events categorized as adverse events to a system organ class and a preferred term. The severity of each adverse event will be graded using (CTCAE) version 4.03 ([Appendix C](#)).

Subject incidence of all treatment-emergent adverse events, serious adverse events, grade 3 or higher, treatment-related, serious treatment-related, adverse events leading to withdrawal of investigational product, and fatal adverse events will be tabulated by system organ class and preferred term by dose level.

Subject incidence of DLTs will be summarized by dose level and preferred term using the DLT Evaluable Analysis Set.

9.6.2 Laboratory Test Results

The analyses of safety laboratory data will include summary statistics at the scheduled time points by dose cohort. Shifts in CTCAE grades of safety laboratory parameters between baseline and the worst post-baseline value for select blood chemistry analytes (creatinine, total bilirubin, aspartate aminotransferase [AST], alanine aminotransferase [ALT], and alkaline phosphatase [ALP]) and hematology analytes (hemoglobin, platelet count, total neutrophils) will be tabulated by dose cohort.

A summary of potential hepatotoxicity by Hy's Law will be tabulated. The criteria are defined as AST or ALT > 3 times upper limit of normal (ULN), total bilirubin \geq 2 times ULN, and ALP < 2 times ULN for baseline and on study assessed within 7 days.

Subject incidence of troponin elevation will be summarized.

9.6.3 Vital Signs

Vital signs (systolic / diastolic blood pressure, heart rate) over time and change from baseline will be summarized.

9.6.4 Physical Measurements

The physical measurement to each scheduled assessment time point will be provided.

9.6.5 Electrocardiogram

All on-study ECG data including PR, QRS, QT, RR, QTcB, and QTcF interval will be summarized.

Summaries over time and/or changes from baseline over time will be provided for all ECG parameters.

Subjects will be categorized into the following groups per their maximum change from baseline in QTcB and QTcF. Unscheduled assessments will be included in the determination of the maximum change.

- ≤ 30 msec
- $>30 - 60$ msec
- >60 msec

The number and percentage of subjects in each group will be summarized.

Subjects will also be categorized into the following groups per their maximum post baseline QTcF. Unscheduled assessments will be included in the determination of the maximum post baseline value.

- ≤ 450 msec
- $>450 - 480$ msec
- $>480 - 500$ msec
- >500 msec

The number of subjects in each group will be summarized for each dosing group.

In addition, the relationship between PK concentration of AMG 397 and change from baseline in QTcF may be explored graphically.

Analysis of the relationship between AMG 397 serum concentrations and change from baseline in QTcF will be conducted and plots of the relationship between AMG 397 serum concentrations and change from baseline in QTcF will be provided.

9.6.6 Antibody Formation

The incidence of subjects who develop anti-AMG 397 antibodies at any time will be tabulated.

9.6.7 Exposure to Investigational Product

Descriptive statistics will be produced to describe the exposure to AMG 397 by dosing schedule. Number of cycles initiated, number of doses, duration of treatment, average dose delivered per day, average dose delivered per treated week and cumulative dose will be summarized. Subject incidence of dose modification along with the reason for dose modification will be summarized.

A listing of the unique manufacturing lot numbers, and a listing of the subjects administered each manufacturing lot number will be provided.

9.6.8 Exposure to Other Protocol-required Therapy

Descriptive statistics will be provided to describe the exposure to azacytidine and dexamethasone. The number of cycles initiated, completed, discontinued, the duration of therapy and total dose will be summarized. Subject-level data may be provided instead of the summary if the subject incidence is low or single dose is given.

9.6.9 Exposure to Concomitant Medication

The number and proportion of subjects receiving concomitant medications will be summarized by preferred term as coded by the World Health Organization Drug (WHO DRUG) dictionary.

9.7 Analyses of Exploratory Endpoints

Analyses of exploratory endpoints may include, but not limited to, biomarkers, pharmacodynamics biomarker measurements, and genomic aberrations.

Identification of metabolite(s) of AMG 397 in plasma and the relationships between PK/PD for safety and efficacy may also be explored.

Details of the exploratory analysis will be provided in a supplemental analysis plan.

9.8 Other Analyses

9.8.1 Analyses of Pharmacokinetic Endpoints

PK parameters will include, but are not limited to, C_{max} , T_{max} , AUC, CL and $t_{1/2}$. These parameters will be estimated using standard non-compartmental PK methods and summarized by dose groups using n, means, standard deviations, medians, coefficients of variation, geometric mean, minimums and maximums.

PK analyses will be provided by the Department of Clinical Pharmacology, Modeling & Simulation (CPMS). Details regarding the analyses will be provided in a separate analysis plan by CPMS.

